9.2.2.2. Number of villages required for prevalence comparison

We assume an average *P. falciparum* prevalence of 16% in group 1 villages using reference assay. Before/after comparison at village level will use samples from the same village but not necessarily the same individuals (correlation between paired observations set to 0). The sample size was calculated assuming 60 samples per cluster (the minimal number of samples collected at M12), an intra-cluster correlation coefficient of 0.15, the sample size required to identify a 50% decrease 12 months after intervention compared to baseline is 43 clusters for alpha=0.05 and 1-beta=0.8.

9.2.3. Sample size for retrospective incidence comparison between MSAT and MDA

If comparing 50 MSAT villages and 50 MDA, we will be able to differentiate MSAT from MDA efficacy if MSAT achieves around 50% of MDA impact on incidence or less.

The average village size was 190 inhabitants (coefficient of size variation=0.64) with an intra-cluster correlation coefficient of 0.12 (estimated using incidence series) and MDA was already completed in 60 villages. The 10 villages in which MDA was conducted based on prevalence values that will be the furthest

from what will be measured during the MSAT campaign will be excluded. Villages receiving MSAT after MDA will be excluded from MSAT group. With a comparison of 50 MSAT, it will be possible to detect a difference in incidence rate of 50/1000/year between the two groups (with alpha=5% and power=80%). This would correspond to a reduction of incidence by only 40% after MSAT (70 cases/1000/year after compared to 125 before). With MDA, 80% incidence reduction was achieved: the average cumulative incidence during the first year after MDA was 20 case/1000/year, compared to 125 before.

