9.2.1. Sample size for stepped-wedge comparison of incidence decrease following MSAT

MSAT will be implemented in 60 villages with high 1-year cumulative incidence of *P. falciparum* clinical cases in 6 waves of 10 villages (1 wave per semester). Assuming a baseline cumulative incidence of 250 cases/1000/year, a population of 190 inhabitants per village with a 0.49 coefficient of variation in cluster size and an intra-cluster correlation coefficient of 0.12, the expected detectable difference between villages with and without intervention is <25 cases/1000/year for alpha=0.01 & beta=0.9.

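### Sections 9.2.1 and 9.2.3 assume different pre-MSAT incidences (250 and 125 per 1000 per year) without reconciling them, and the MSAT-versus-MDA separation limit in 9.2.3 holds only if both groups start at 125

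*Combined protocol and SAP*

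**What the plan says.** Section 9.2.1 sizes the primary stepped-wedge analysis for 60 group 1 villages: "Assuming a baseline cumulative incidence of 250 cases/1000/year", with 190 inhabitants per village and an intra-cluster correlation of 0.12.

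Section 9.2.3 sizes the retrospective comparison of 50 MSAT villages with 50 MDA villages. MSAT villages that had MDA first are left out. Village size and intra-cluster correlation are the same as in 9.2.1; the coefficient of variation of village size is 0.64 instead of 0.49. It gives a detectable difference of 50 per 1000 per year at 5% alpha and 80% power, and adds: "This would correspond to a reduction of incidence by only 40% after MSAT (70 cases/1000/year after compared to 125 before". For MDA it reports 125 before and 20 in the first year after. Its headline is that "we will be able to differentiate MSAT from MDA efficacy if MSAT achieves around 50% of MDA impact on incidence or less".

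The tertiary outcome in section 4 is incidence and prevalence before and after each intervention. Section 9.3 gives no model for the MSAT-versus-MDA incidence comparison.

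**The concern.** The 50 MSAT villages of 9.2.3 come from the same programme as the 60 villages of 9.2.1, yet their assumed starting incidence differs by a factor of two. The power calculation uses only rates after intervention. Turning a rate of 70 into a percentage reduction, and then into a share of MDA's impact, requires a starting value, and 9.2.3 uses 125 for both groups.

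Unequal starting values are plausible. MDA villages were chosen on prevalence (section 3), whereas group 1 villages are chosen on incidence above 84 per 1000 per year (sections 5 and 6.1.1). The only matching in 9.2.3 is on prevalence. If the groups start at different levels, a gap in after-rates no longer measures relative efficacy, and whether MSAT can stand in for MDA could be judged partly on where the villages began.

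**Working it through.** **Inputs.** From 9.2.3: 50 villages per group, 190 inhabitants, coefficient of variation 0.64, intra-cluster correlation 0.12, alpha 5%, power 80%, MDA 125 to 20, MSAT 125 to 70. From 9.2.1: 250 before MSAT. Sidedness is not stated; two-sided is assumed.

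**1. Reproducing the plan.**
- Design effect = 1 + ((0.64² + 1) × 190 − 1) × 0.12 = 33.02.
- Effective size per group = 50 × 190 / 33.02 = 287.7 person-years.
- With Poisson variance, SE of 0.07 − 0.02 = √(0.09 / 287.7) = 0.0177. Power = Φ(0.05/0.0177 − 1.96) = 0.81. The rate detectable against 20 with 80% power is 69.4, a difference of 49.4; 49.1 villages per group are needed.
- With binomial variance: power 0.83, detectable rate 67.7, 46.7 villages per group.

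The stated 50 per 1000 and 50 villages reproduce.

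**2. From after-rate to share of impact.** From 125, MSAT falls by 1 − 70/125 = 44% (stated as 40%) and MDA by 1 − 20/125 = 84% (stated as 80%). The share is 0.44/0.84 = 52%, which matches the headline. The starting value enters only here.

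**3. Equal efficacy, unequal start.** If MSAT starts at 250 and also achieves 84%, it leaves 250 × 0.16 = 40, against 20 for MDA. SE = √(0.06 / 287.7) = 0.0144 and 0.02/0.0144 = 1.385, so a raw after-rate test is significant in about 28% of repetitions (29% with binomial variance).

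**4. Half of MDA's impact from 250.** A 42% fall leaves 250 × 0.58 = 145. Against 20, z = 0.125/√(0.165/287.7) = 5.2, power above 99.9%. Against 40 (MDA also starting at 250), z = 0.105/√(0.185/287.7) = 4.1, power about 99%.

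**5. The limit on the rate-ratio scale.** Let b be the before-rate and a the after-rate. The limit solves ln[(a_MSAT/b_MSAT)/0.16] = 2.80 × SE, where SE² = (1/287.7) × (1/a_MSAT + 1/a_MDA), with 1/b_MSAT + 1/b_MDA added inside the bracket when baseline variance is counted. Before and after are taken as uncorrelated within villages, which is an assumption. In each cell the first figure omits baseline variance and the second includes it.

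| Start, MSAT / MDA | MDA after | MSAT after, at limit | Ratio of rate ratios | Share of MDA impact |
|---|---|---|---|---|
| 125 / 125 | 20 | 75, 86 | 3.7, 4.3 | 48%, 37% |
| 250 / 125 | 20 | 139, 157 | 3.5, 3.9 | 53%, 44% |
| 250 / 250 | 40 | 106, 116 | 2.6, 2.9 | 69%, 64% |

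These are guides. At 20 per 1000 the effective count is only 287.7 × 0.02 = 5.8 cases, so the normal approximation is rough. Positive before/after correlation within villages would reduce the variance and raise the limits.

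**The case against.** The strongest defence is that 125 is the observed MDA baseline carried over as a common starting point, a reasonable simplification for planning. The village sets are not identical: 9.2.1 covers 60, and 9.2.3 takes 50 without prior MDA. Both 125 and 250 exceed the entry threshold of 84. Section 9.2.3 drops the 10 MDA villages furthest from the MSAT villages in prevalence, which is an attempt at comparability. Section 4 defines a before-and-after outcome over the whole incidence series, so the after-only contrast is a planning shortcut and need not be the analysis. MDA is already complete, and the objective is tertiary.

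Most of this stands and limits the point. But matching on prevalence does not equalise incidence, nothing suggests that leaving out villages with prior MDA would halve the starting incidence, and no section explains the two values. The before-and-after outcome in section 4 is itself a reason to size the comparison on that scale.

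A reader might infer that the half-impact claim is false or underpowered. Step 4 shows the opposite for the raw contrast.

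A reader might also take 28 to 29% as the error rate of the planned analysis. The documents do not prescribe the raw after-rate test for analysis, so the figure applies only if that test were used.

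**Conclusion.** The inconsistency is real: two unreconciled baselines, and a separation limit that follows from the raw contrast only when both groups start at 125. The documents do not show which baseline is right, so it should not be inferred that 250 is correct and 125 an error.

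On the rate-ratio scale, with the plan's design effect, Poisson variance, 80% power and no before/after correlation, the limit is about 37 to 48% of MDA's impact if both groups start at 125, 44 to 53% if MSAT starts at 250 and MDA at 125, and 64 to 69% if both start at 250. The headline of about half may therefore survive, but it has to be derived on a scale that separates baseline from efficacy.

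Two tempting replacement figures do not hold:
- **86% of MDA's impact** (0.72/0.84, since 70 is a 72% fall from 250). This reuses the raw contrast that unequal baselines undermine. On the ratio scale, ln(0.28/0.16) = 0.56 with SE 0.47 to 0.51, which gives only about 19 to 22% power.
- **A primary detectable effect of 25/125 = 20%.** The 25 per 1000 was derived at 250 and shrinks with the baseline. Rough scaling gives 25 × √(0.125 × 0.875 / (0.25 × 0.75)) = 19 (about 15%), or 25 × √0.5 = 18 (14%) with Poisson variance. Section 9.2.1 needs re-running, not rescaling.

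The consequence is mainly one of interpretation, for a tertiary objective. The link to the primary analysis is that its sample size uses the 250.

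**What to change.** 1. Take one pre-MSAT incidence for group 1 from the METF 12-month incidence list that already selects the villages (sections 5 and 7.1), or state why two values are needed.
2. Re-run 9.2.1 and 9.2.3 with it.
3. Restate 9.2.3 as the smallest detectable ratio of after/before rate ratios, MSAT versus MDA, giving the assumed starting incidence of each group and the assumed within-village before/after correlation. This matches the outcome in section 4.
4. Replace the percentage reduction and the share of MDA impact with the figures from that calculation. Do not insert 86%, and do not convert 25 per 1000 to 20%.

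The cost is two re-run sample-size calculations, and a stated figure may change. No villages or data collection are added.

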9.3. Analysis of Outcome Measures

Primary outcome: stepped-wedge comparison of incidence.

The incidence comparison will be conducted over a 2-year series of weekly incidence data, corresponding to 12 months before and 12 months after MSAT intervention. A generalized additive multilevel mixed model will be used to adjust for location, season, and temporal trend due to MP activity using uni-(seasonality, duration of MP activity in the village) or bivariate (latitude and longitude) splines, including random intercept and slopes at village level. MSAT intervention will be included in the model as a 0-1 variable. The incidence rate ratio obtain for this variable will quantify the average decrease in incidence after MSAT campaign compared to before.

Secondary outcome: before-after comparison of prevalence

For each village, the fractional change in prevalence before MSAT and 12 months after will be calculated and compared to 0% change. This change will be compared to the fractional change observed after MDA.

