Figure 3: Average *P. falciparum* and *P. vivax* incidence in hotspots before and after MDA, centered on date of MDA. A marked decrease in *P. falciparum* incidence after MDA can be observed, in spite of an increase in incidence around 15 months after MDA. This increase is related to 5 hotspots (out of 52 followed up to M18) showing an incidence above 50 case/1000 for 1 month during the second year after MDA. This increase did not persist further.

In this project, we aim at an operational research deployment of URDT-based MSAT in the METF elimination program. This intervention will be tested in two types of setting, which correspond to two arms in this study. In group 1, MSAT will be used in a programmatic setting in order to decrease the reservoir of asymptomatic carriers in high incidence villages (following the same principles and objective as previously deployed MDA interventions). In group 2, we take advantage of the lighter framework of MSAT to use it as a reactive intervention in order to respond to malaria outbreaks in low to intermediate incidence villages. The MSAT intervention will be preceded with community-level consent and community engagement (CE) activities. MSAT will be conducted over a period of approximately 1 week in each hamlet, village or group of villages, and will consist in administering a *P. falciparum* URDT to all individuals agreeing to participate. A limited subgroup (expected 5-25%) will be found positive and receive supervised treatment over 3 days for the standard regimen (DP to cure asexual stage infection + single low-dose primaquine to destroy gametocytes). After this intervention, the incidence of clinical falciparum episodes will be monitored by the village MP. In group 1, a comparison of the prevalence at baseline and 12 months after MSAT intervention will be performed through a second URDT survey, in addition to which both baseline and 12-month surveys will include the collection of a 50 μ L capillary blood sample for reference detection in the laboratory.

The intervention will be evaluated primarily on its ability to reduce yearly cumulative incidence of clinical falciparum malaria compared to year before intervention. Additional evaluations of the impact of MSAT will include: in group 1, comparison of asymptomatic infection prevalence; and in group 2, modifications of the shape of the incidence curve following intervention.

Potential risks and benefits for participants

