5. STUDY DESIGN

Stepped-wedge open-label, non-randomized, cluster intervention.

This study will be performed in clusters (hamlet (isolated group of household, village, or group of village). The intervention will be conducted in two types of clusters, both corresponding to locations where an excess of case was detected.

Group 1: Sustained high incidence clusters, characterized by a yearly cumulative incidence >84 cases/1000/year

Villages in group 1 will be attributed an intervention a given year based on the cumulative incidence over the previous 12 months (METF stratification January, including the last 2 transmission seasons). The order of intervention will be decided based on logistic constraints and highest incidence.

Group 2: Focal transmission clusters, corresponding to locations where an epidemic alert has been signalled and confirmed (see definition of thresholds).

*Villages in group 2 will be attributed an intervention based on *P. falciparum* incidence in the previous 4 weeks. In near-0 transmission area, an intervention will be conducted in each likely source location of transmission of a locally acquired case. In the other areas (METF1+METF2), the intervention will be triggered when the incidence is above the pre-defined epidemic threshold.*

In each cluster, all inhabitants will be invited to undergo an URDT test to identify their infection status, and will receive the appropriate treatment according to their characteristics. Information on village inhabitants absent during the MSAT activities will be obtained from village population lists provided by the village headman and from household member declarations. During the URDT screening, all individuals will receive a unique identifying number that will be used to record demographic data in the MSAT paper logbook and to label URDT and reference sample.

Before and after MSAT intervention, incidence of clinical malaria episodes will be recorded at the MP (1 or several) serving the cluster receiving the intervention. No individual data will be collected to link clinical case participation, infection status and incidence of clinical episodes.

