6.1.1. Group 1: sustained high incidence villages

Villages classified as high incidence, low probability of elimination (*P. falciparum* cumulative incidence >84 cases/1000/year, in spite of >1 year of functioning malaria post) will be eligible to be included in group 1. Villages in this group will be addressed by MSAT waves of 10-15 villages.

Villages will be included in a given wave based on accessibility to the team and proximity from each other, as well as requirements for the program impact. Wave 1 will include 5 villages and be conducted during first semester 2018, after which a maximum of two waves will be conducted per semester.

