7.4. Randomisation, blinding and code-breaking

No randomization will be conducted. Villages with sustained high incidence will be assessed every 6 months and prioritized based on accessibility/feasibility. As much as possible, all villages from a given area will be addressed at the same time in order to maximize impact of interventions.

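### The primary before/after incidence ratio is taken in clusters chosen for high incidence largely inside the before-year, so it need not equal 1 when MSAT has no effect

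*Combined protocol and SAP*

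**What the plan says.** Section 3 says MSAT will be "evaluated primarily on its ability to reduce yearly cumulative incidence of clinical falciparum malaria compared to year before intervention". Section 9.3 fits a generalised additive mixed model "over a 2-year series of weekly incidence data, corresponding to 12 months before and 12 months after MSAT intervention". It has splines for season, location and duration of malaria post (MP) activity, and village random intercepts and slopes. The coefficient of a 0-1 MSAT term "will quantify the average decrease in incidence after MSAT campaign compared to before". The Synopsis lists groups 1 and 2 under the primary objective.

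Section 7.4 rules out randomisation. Entry rules are as follows:
- **Group 1.** Section 5: "Villages in group 1 will be attributed an intervention a given year based on the cumulative incidence over the previous 12 months". Section 6.1.1 sets the threshold at more than 84 cases/1000/year, and section 7.1 revises the list twice a year.
- **Group 2.** Section 5 uses "incidence in the previous 4 weeks". Section 6.1.2.1 acts on one notified case, and section 6.1.2.2 on an outbreak alarm confirmed as local transmission. Section 9.2 notes that group 2 responses are often to a single case.

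The order of treatment in group 1 is described in three ways. Section 5: "The order of intervention will be decided based on logistic constraints and highest incidence". Section 6.1.1: "Villages will be included in a given wave based on accessibility to the team and proximity from each other", together with programme needs. Section 7.4: "prioritized based on accessibility/feasibility".

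The analysis window also varies. Section 4 gives follow-up from MP opening to the end of the study. Section 9.1 mentions an analysis of the whole MP follow-up, but its sentence breaks off in the available text.

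**The concern.** A cluster picked because its recent incidence was high will tend to show lower incidence later, whether or not it was treated. When the picking period is also the baseline, this regression to the mean enters the IRR. Adjusting for season, place and MP duration does not target it, because the selection is on the outcome itself. In group 2 a second force acts the other way: a trigger that marks the start of local transmission may be followed by more cases.

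At stake is whether a primary IRR below 1 can be read as an MSAT effect, and in group 2 whether an IRR on either side of 1 carries any such meaning.

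**Working it through.** **The plan's own figure (group 1, section 9.2.1).** Inputs: 60 villages, 6 waves of 10, baseline 0.25, intra-cluster correlation 0.12, 190 people per village, size CV 0.49, alpha 0.01, with beta=0.9 read as 90% power.
- Between-village variance: 0.12 × 0.25 × 0.75 = 0.0225. Effective size: 190/(1 + 0.49²) = 153.2. Village-period variance: 0.88 × 0.1875/153.2 = 0.001077.
- The Hussey-Hughes variance with 7 periods gives SE = 0.00567. Detectable difference: (2.576 + 1.282) × 0.00567 = 0.0219, or 21.9/1000/year. The stated bound of under 25 reproduces.
- As a ratio: (250 − 25)/250 = 0.90.

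**Group 2, no effect, trigger = first case since study start.** Let L be the constant yearly case rate (assumed; the plan gives none). The time T to the first case is exponential. The before-year holds the trigger case plus background cases from the part of that year before study start, so its expectation is 1 + L × E[(1 − T)+] = 1 + L − (1 − e^−L) = L + e^−L. The after-year expectation is L.
- Ratio L/(L + e^−L): L = 0.1 gives 0.10, 0.5 gives 0.45, 1 gives 0.73.
- Leaving out the trigger case gives L/(L + e^−L − 1), which is 1/0.368 = 2.7 at L = 1. Dropping the trigger therefore replaces one bias with another.
- With R secondary cases per case (assumed) and low rates, the ratio is about (L + R)/(1 − R). At L = 0.1 this is 0.4/0.7 = 0.57 for R = 0.3 and 0.6/0.5 = 1.2 for R = 0.5. Simulation with a 30-day generation gap and MSAT 7 days after the case gives 0.55 and 1.16.
- A trigger of a 4-week count above its 90th percentile (section 6.1.2.2, given there as an example) gave 0.85 to 1.6 in simulation, depending on assumed rates and autocorrelation.

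**Group 1, no effect.** With lists redone every six months, the qualifying 12 months overlap the before-year by roughly 6 to 12 months.
- Between-village CV from the plan's intra-cluster correlation: at 250/1000, √0.0225/0.25 = 0.60. At 125/1000, the level before mass drug administration (MDA) in section 9.2.3, √(0.12 × 0.125 × 0.875)/0.125 = 0.92.
- Simulation: lognormal village rates, with 10 to 50% of that variance transient (assumed). Poisson counts, the 84/1000 rule reapplied each semester, and 10 villages treated per semester for 6 semesters.

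| Order | Pool mean /1000 | Crude after/before ratio |
|---|---|---|
| Unrelated to incidence | 250 | 0.98–1.00 |
| Unrelated to incidence | 125 | about 0.89–0.96 |
| Highest first | 250 or 125 | about 0.76–0.95 |

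A separate run with 75, 120 and 200 candidates and semester autocorrelation 0.5 gave 0.99–1.00, 0.90–0.96 and 0.79–0.95, inside these ranges.

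**After adjustment.** Highest-first order gave 0.73 to 0.88 with fixed village effects, but 0.79 to 1.09 with a random intercept and random time slope. Section 9.3 does not say what its slopes are on, so the adjusted size cannot be fixed from the plan.

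**The case against.** The strongest reply is that section 9.3 describes a stepped-wedge comparison. Waves are staggered, so treated and untreated village-time overlap, and the mixed model borrows from that overlap. Sections 4 and 9.1 also point to a whole-series analysis. In one check of highest-first order, the crude ratio moved from 0.82–0.94 with 12 months before to 1.00–1.05 with 24 months before. Both points stand in part. But section 9.3 defines the primary analysis on the two-year window and names no term for selection, and the section 9.1 sentence cannot be read to its end. It follows only that no readable passage addresses the problem.

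Several stronger readings are tempting, and the documents do not support them:
- **That group 1 is safe if order ignores incidence.** The threshold itself selects on the outcome. Its effect is negligible at a pool mean of 250/1000 but not nearer 84/1000.
- **That the group 1 bias exceeds the effect the trial was sized for.** Setting it against 0.90 is not like for like. Section 9.2.1 uses 250/1000 as the baseline of treated villages. With 250/1000 as the pool mean and highest-first order, treated villages averaged about 305 to 530/1000.
- **That both groups enter one model.** The Synopsis places both under the primary objective, but no passage says they are pooled. Group 2 also has its own secondary outcome on seasonal peaks.
- **That the smooth decline under MP activity is the problem.** The MP-duration spline addresses that.

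**Conclusion.** The concern holds. The primary IRR compares each cluster with a year that helped to select it, and its value under no effect is not known to be 1.

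For group 2 the direction itself is open, so the before/after IRR is not evidence of effect either way. For group 1 the crude no-effect ratio lies below 1 through the entry threshold: slightly at a pool mean of 250/1000, by about 4 to 11% at 125/1000. It falls further as far as order follows highest incidence, which section 5 names and sections 6.1.1 and 7.4 do not.

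The direction of the crude group 1 bias is firmer than its size. The size depends on the assumed candidate pool and transient variance share, and after adjustment on random slopes that the plan leaves undefined. Group 2 values depend on assumed case rates and onward transmission. The sample-size figure in section 9.2.1 is not in dispute.

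**What to change.** 1. Report group 1 and group 2 IRRs separately, with no pooled headline.
2. Label the group 2 before/after IRR descriptive, unless alerts that met the same trigger without MSAT are available as comparators. Do not simply drop the trigger period.
3. For group 1, keep the section 9.3 model and state what its random slopes are on. Beside it, prespecify a sensitivity analysis against concurrent time in listed, not-yet-treated villages that met the same 84/1000 rule. Stratify by list and calendar period, adjust for qualifying-window incidence and location, and censor each comparator at its own MSAT. If this contrast does not support a primary-model effect, describe that effect as possibly regression to the mean.
4. Reconcile the ordering statements in sections 5, 6.1.1 and 7.4, and the analysis window in sections 4, 9.1 and 9.3. Record why each village takes its place in the order.

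**Cost.** The change needs SAP wording and one analysis of weekly MP data already collected (section 7.6.2). The real price is precision. In simulation at a pool mean of 250/1000, without location adjustment, the SD of the concurrent log IRR was 0.049–0.105 with order unrelated to incidence and 0.050–0.193 highest first. At alpha 0.01 and 90% power, exp(−3.86 × SD) gives a detectable IRR of about 0.67–0.83 and 0.47–0.82, against 0.90 in section 9.2.1. The contrast can also lean towards no effect, with a null IRR up to 1.14 under highest-first order. It should therefore not be a veto: requiring both analyses to agree gave power as low as 21% at a true IRR of 0.8. Comparators will be few in late waves or with the faster rollout that section 6.1.1 allows, and may lie in other areas because section 7.4 treats neighbouring villages together. Group 2 may be left without a causal estimate.

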4. OBJECTIVES AND OUTCOME MEASURES

Objectives	Outcome Measures	Timepoint(s) of evaluation of this outcome measure (if applicable)
Primary Objective To measure the impact of URDT-based MSAT on P. falciparum incidence at village-level.	Adjusted incidence rate ratio before/after MSAT	Follow-up from MP opening to end of study
Secondary Objectives 1) To measure the impact of MSAT on prevalence of P. falciparum infection in malaria hotspots	1) Prevalence of P. falciparum infection measured in the village by URDT and by reference method (group 1)	1) Comparison between M0 survey (during MSAT) and M12 survey (12 months after)
2) To measure the impact of reactive MSAT on incidence of seasonal malaria peaks / outbreaks.	2) Change in the incidence dynamics over the transmission season (group 2)	2) Duration and height of seasonal peak before, during and after reactive intervention
3) Feasibility of MSAT as a programmatic tool and as a reactive strategy.	3) Coverage of village population with intervention	3) coverage based on census conducted before/during MSAT
4) % of infections treated compared to infections detected by reference method	4) % of P. falciparum positive samples by reference method which were positive by URDT and treated; % of P. falciparum negative samples by reference method which were positive by URDT and treated (group 1)	Group 1 only
Tertiary Objectives Retrospective comparison of MSAT versus MDA on prevalence and incidence of P. falciparum malaria	Cumulative incidence of falciparum malaria episodes before and after MDA/MSAT; prevalence of falciparum infection before and after MDA/MSAT	Entire incidence series

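### Villages with earlier mass drug administration are excluded only from the tertiary comparison; the primary MSAT model neither excludes them nor adjusts for time since MDA

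*Combined protocol and SAP*

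**What the plan says.** Section 9.2.3 (the retrospective MSAT-versus-MDA comparison) reports that "MDA was already completed in 60 villages" and sets the rule "Villages receiving MSAT after MDA will be excluded from MSAT group". On the effect of MDA it says that "the average cumulative incidence during the first year after MDA was 20 case/1000/year, compared to 125 before".

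The rule is not repeated elsewhere. Group 1 selection (6.1.1) requires more than 84 cases/1000/year "in spite of >1 year of functioning malaria post". Group 2 selection (5, 6.1.2) rests on recent cases or outbreak alarms and has no annual floor. Section 7.8 drops a village only if MSAT cannot be done or its population changes by half or more. None of these mentions MDA.

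The primary model in 9.3 is set up to "adjust for location, season, and temporal trend due to MP activity", "including random intercept and slopes at village level"; the variable carrying the slopes is not named. "MSAT intervention will be included in the model as a 0-1 variable".

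The window is described in more than one way. Section 9.3 uses 12 months on each side of MSAT. The primary outcome row in Section 4 gives "Follow-up from MP opening to end of study", and 9.1 also plans adjusted estimates from the whole MP follow-up.

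**The concern.** The primary outcome is a before/after rate ratio within villages. It measures MSAT only if no other large intervention moves incidence within the same series. MDA is such an intervention, and the plan itself foresees that some villages will have had both.

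MP duration runs from the opening of the post and season runs with the calendar, so neither is tied to the date of MDA. A random intercept removes a constant difference between villages, and a random slope may remove some steady drift. Neither represents a step down at MDA or a rise and fall some months later. What they miss can be attributed to the MSAT indicator.

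Two features make overlap plausible. MDA was given to hotspots, and Section 3 places 52 of 69 hotspots in the one township where Section 6.1 says transmission remains heterogeneous.

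**Working it through.** **The plan's own figures (9.2.3).** The inputs are 190 inhabitants, coefficient of variation 0.64, intra-cluster correlation 0.12, rates 70 and 20/1000/year, alpha 5% (taken as two-sided) and power 80%.

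- Design effect = 1 + ((0.64² + 1) × 190 − 1) × 0.12 = 33.0.
- Villages per group = (1.960 + 0.842)² × (0.07 + 0.02) / 0.05² × 33.0 / 190 = 49.1, which agrees with the stated 50.
- The MDA effect is 20/125 = 0.16, a fall of 84% (the text says 80%).

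**Which villages can carry an MDA step into the 12-month window of 9.3.** Suppose a village at 125 falls to 20 at an MDA m months before MSAT, treated as an immediate step. Its 12-month incidence is 125(12 − m)/12 + 20m/12. This exceeds 84 only if m < 12 × (1 − 64/105) = 4.7 months. A village held at 20 for the whole year cannot enter group 1, but could enter group 2.

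**Pooled effect in that window if MSAT does nothing.** Let f be the share of villages with earlier MDA (assumed, since it is not stated). The others are flat at 250/1000/year, the 9.2.1 baseline. The case-weighted ratio is ((1 − f) × 250 + f × post) / ((1 − f) × 250 + f × pre).

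- MDA 3 months before MSAT: pre = 125 × 9/12 + 20 × 3/12 = 98.75 and post = 20.
  - f = 10%: (225 + 2)/(225 + 9.875) = 0.97.
  - f = 25%: (187.5 + 5)/(187.5 + 24.69) = 0.91.
  - If the model averages villages on the log scale, (20/98.75)^f gives 0.85 and 0.67.
- MDA effect waning from the eligibility threshold back to 125: pre = 84 and post = 125.
  - f = 10%: (225 + 12.5)/(225 + 8.4) = 1.02.
  - f = 25%: (187.5 + 31.25)/(187.5 + 21) = 1.05.
- MDA effect stable (84 then 84, or 20 then 20): 1.00.

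For scale, the detectable difference in 9.2.1 is below 25 on a baseline of 250, or 10%.

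**Series from MP opening (Sections 4 and 9.1).** These are crude single-village ratios with no MSAT effect. They assume one year at 125 before MDA and MDA 24 months before MSAT.

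- Incidence stays at 20 in both post-MDA years and afterwards: before = (125 + 20 + 20)/3 = 55, ratio 20/55 = 0.36.
- Incidence is 20 in the first year, then about 84 in the second year and afterwards: before = (125 + 20 + 84)/3 = 76.3, ratio 84/76.3 = 1.10.

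In the 12-month window both ratios are 1.00. The longer window therefore creates a bias that the shorter one avoids, and its sign depends on the course after MDA. The spline and random slopes might absorb part of it, and the pooled effect would be diluted by f.

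**Timing.** MDA in the 40 villages of Figure 2 ran from January 2015 to April 2016. MSAT starts in the first semester of 2018, at least 20 months later. Some hotspots had not been addressed by April 2017, and no later MDA dates are given.

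**The case against.** The strongest reply is that the documented dates leave little room for a recent MDA. For the 40 dated villages no MDA falls inside the 12 months before MSAT. The Figure 3 caption refers to 52 hotspots followed to month 18; if that means completed follow-up, at most 60 − 52 = 8 of the MDA villages had less. The group 1 threshold keeps suppressed villages out of that group. This stands, and it limits the problem under the 9.3 window to a few late MDAs or to rebounds.

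The rebound evidence is also thin: 5 of 52 hotspots, above 50/1000 for one month, and not persisting. That is not a general return of transmission. It still shows that the course after MDA need not be flat.

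A reader might infer that the fall from 125 to 20 passes in full into the primary rate ratio, or that all 60 MDA villages affect it. The documents support neither reading. The fall is the average first-year effect of MDA in MDA villages, and the number that will also receive MSAT is not given. Nor is the model wholly without protection, since a stable MDA effect cancels through the village intercept.

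Finally, the sentence in 9.1 on adjusted estimates breaks off in the available text, and the village flow chart in Appendix A is not shown. A further covariate or selection step could be stated there. The covariates that 9.3 lists for the primary model do not include MDA.

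**Conclusion.** The gap holds. The plan foresees MSAT after MDA, protects only the tertiary comparison, and gives the primary model no MDA exclusion and no MDA-specific adjustment.

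The direction is not fixed. A recent MDA, or a transient rebound that subsides, exaggerates the MSAT benefit. Waning of the MDA effect, or suppressed post-MDA time in the 'before' period, hides it. With a series from MP opening, the MDA fall itself lies in the 'before' period, so the exposure is greatest there.

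The size cannot be estimated from the documents. The values 0.97 and 0.91 rest on assumed overlaps of 10% and 25%, MDA 3 months before MSAT, and all other villages flat at 250. They show that a modest overlap could matter against a 10% detectable difference; they do not forecast the bias. If MDA effects are stable over the window, or no MSAT village had MDA, there is no bias. This is a correctable omission in the analysis plan and does not invalidate the design.

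**What to change.** - In 9.3, add a time-varying time-since-MDA term to the primary model (for example a spline or yearly categories, zero for villages without MDA). Alternatively, extend the 9.2.3 exclusion to the primary analysis.
- Report the estimate in MDA-naive villages as a sensitivity analysis. It is needed even with the added term, because a common time-since-MDA curve describes the average course and not a rebound in a few villages.
- State how many group 1 and group 2 villages had MDA, and when.
- Reconcile the analysis windows in Sections 4, 9.1 and 9.3, and name the one used for the primary rate ratio.

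The cost is one extra model term, or slightly fewer villages if exclusion is chosen. The programme that ran the MDA campaigns should already hold their dates.
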